**Benefits:**

There are no benefits to you from your taking part in this research. We cannot promise any benefits to others from your taking part in this research. However, possible benefits to others include pain relief and possibly shorter hospital stay with decreased risk of complications. The only alternative post-operative pain treatment options include intravenous or oral opioids. During the study period, any subject who prefers not to be involved in this study will be treated appropriately as determined by the surgeon and anesthesiologist. There will be no alteration in the post-operative program for those that decline enrollment in this study.

No parties will receive any specific direct benefits from this study with the exception of the patient. The physician and medical community at large may indirectly benefit from learning more about the post-operative pain options for these patients.

**Precautions and corrective actions:** All treatment arms will have the same post-operative protocol. All complications will be noted by the operating physician and reported to the IRB and research staff. Appropriate records will be made in the patient chart and the patient will be treated as needed by the operating physician.

**Project Medications:** All medications will be provided by the hospital pharmacy, and will be noted in the medicine administration record in the chart. No experimental medications will be evaluated in this study.

**Specimens to be collected:** None

**Data collection:** The surgeon, anesthesiology staff, and research staff will collect data. The data will be comprised of outpatient notes, inpatient records, operative reports, intra-operative photos and assessments, questionnaires, study follow-up evaluations. In addition to the surveys used to measure subjective and objective outcome, other data will be collected during patient interviews including:

- Demographic data
- Age
- Weight
- ASA class
- Type and duration of surgery
- VAS Score at 1, and 6, 24, , 48, , and 72 hours after surgery
- Length of stay in recovery room
- Amount of opioids given preop,intraoperatively and post-operatively
- Rate of conversion to general anesthetic
- Satisfaction with treatment
- Quality of recovery survey on 72 hours post-injection
- OBAS at 72 hours
- Chronic pain (pain disability index) at 3, 6, 12 months
- At 72 hours the following will be recorded:
  - Any persistent need for analgesics
  - Total length of stay
  - Total Use of opioids per day
  - Amount of opioids left over after 3 days
  - Presence of nausea/vomiting in 3 days post operatively
  - Occurrence of any subsequent re-admission over the ensuing 1 month and any complications

The collected data will be compared between groups on a regular basis in order to evaluate the safety and efficacy of the study. All data will be stored in secure locations in the Research Office. Research coordinators working with physicians to collect data at appropriate intervals will ensure complete follow-up. Research coordinators will periodically check physician schedules to ensure that patients being seen for follow-up complete all required questionnaires. Monthly meetings will also be conducted to ensure all patients needing to be evaluated are seen at the appropriate time intervals and that all data is being entered into the appropriate database.

**Data Safety Monitoring:** Authorized study staff and investigators who have gone through HIPAA, CITI, and other data security training through the University of Minnesota will be collecting, managing, and analyzing data. All serious adverse events will be brought forward to the Anesthesia Data Safety Monitoring Board that is comprised of various senior staff anesthesiologists. A formal determination concerning the severity of the risk and the recommended actions required will be submitted in writing to the principle investigator. This report will be submitted to the Institutional Review Board along with the required UPIRTSO documents.

**Statistical Considerations:** The primary outcome measurement used in this study is total opioid use

A sample size of 112 (56 per group) will be enrolled in order to power our study at 80% to detect a 35% decrease in total post-operative opioid usage for our treatment group versus the control with an  $\alpha=0.05$ . This sample size was estimated based on previous estimates for postoperative analgesic consumption from similar trials reported in the Tam (2015) meta-analysis paper.

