### **Secondary Objectives:**

1. To determine if a pectoralis 1 and 2 block with liposomal bupivacaine provides decreased maximal pain scores when compared to incisional bupivacaine infiltration
2. To determine if a pectoralis 1 and 2 block with liposomal bupivacaine provides decreased rate of conversion to general anesthetic when compared to incisional bupivacaine infiltration
3. To determine if a pectoralis 1 and 2 block with liposomal bupivacaine improves quality of recovery score post-operatively when compared to incisional bupivacaine infiltration.
4. To observe the effect on chronic postoperative pain in patients who have breast surgery.

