### **Inclusion criteria assessed during surgery:**

- All patients undergoing partial mastectomy procedures.
- Ages 18-75

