**Exclusion criteria:**

- Patient on chronic anticoagulation
- Pregnant women
- Non-english speaking patients
- Any individuals who are unable to give informed consent
- Any individual with diminished capacity to give informed consent
- Allergy to local anesthetics
- Patients who remain intubated overnight after surgery or who are unable to provide information regarding their pain immediately postoperatively
- Daily use of opioid for more than three weeks
- Significant liver disease, defined as liver enzymes greater than 3x the upper limit of normal
- Lack of patient cooperation including those patients who refuse a MAC anesthetic
- Patient with pectoral muscle involvement of tumor
- Contraindication to regional anesthesia
  - Infection at injection site
  - Inability to guarantee sterile equipment or sterile conditions for the block
  - Patient refusal
  - Severe Coagulopathy or bleeding disorder

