(scores will be evaluated at 1 hr, 2 hr, 6hrs, 24hrs, 48hrs, 72hrs). They will record daily opioid use, any modality related complications, how many phone calls were made regarding pain control and modality related complications. At time period 72 hours a Quality of recovery survey (see appendix) and OBAS (see appendix) survey will be presented to patient. Patients will be offered phone calls for contact, but patients may opt to be contacted via text message if they do not wish to have phones calls. We will provide patients with an additional consent for text messaging if they wish to use this method.

At 3 months, 6 months, and 12 months patients will be called to answer a survey with regards to chronic pain.

Patients will be instructed to take acetaminophen 1000 mg every 8 hours while at home for 3 days. They will be given a prescription of opioid pain medications either oxycodone or hydromorphone and will be instructed to take as needed for pain.

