### **Assessments:**

Post-operatively patients will be evaluated 1 and 2 hr post-operatively by the PACU nurse and 6 hrs post-operatively by a medical student or research coordinator. This person will not be aware of the patient's mode of analgesia. The medical student or research coordinator will evaluate at, 24, 48, and 72 hours post injection +/- 5 hours. If sent home they will be contacted via preferred contact method at, 24, 48, and 72 hours post-operatively. Patients will be asked to rate their pain on scale of 0-10. The amount of opioids used by the patient will be recorded as will any other adjuvant pain medication used. Any modality related complications will be recorded. The patients will be asked at 72 hours post-injection to fill out a quality of recovery and OBAS survey. All complications will be recorded from time of consent to last follow up date. Patients will be called at 3, 6, and 12 months post operatively to fill out a chronic pain survey.

All data will be recorded in a locked encrypted database. Data collection will continue until Postoperative day ( POD ) #3. Should patients be re-admitted to the hospital in the next two weeks (Up to POD #19) for pain a notation will be made in study records. Additional contacts by the research assistant or medical student will continue up until the 3, 6, and 12 month postoperative times.

An analysis of the total cost of analgesics (including patient costs for opioid prescriptions) will be tabulated at the conclusion of the study to determine the most cost effective treatment option as this will be added into the cost of hospitalization including the number of days each patient spent in the hospital.

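### No preoperative pain or disability score is planned, so pain at 3 to 12 months cannot be classed as new or worsened and baseline adjustment is not possible

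*Combined protocol and SAP*

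**What the plan says.** All references are to the combined protocol and SAP.

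- **Secondary Objectives**, item 4: "To observe the effect on chronic postoperative pain in patients who have breast surgery". The Secondary Hypotheses paragraph does not mention chronic pain.
- **Data collection list** (after Benefits): "Chronic pain (pain disability index) at 3, 6, 12 months". The acute entry reads "VAS Score at 1, and 6, 24, , 48, , and 72 hours after surgery". The preoperative entries include demographics, weight, ASA class and the amount of opioid given, but no pain or disability score.
- **Treatment technique**: "At 3 months, 6 months, and 12 months patients will be called to answer a survey with regards to chronic pain". For acute pain, "scores will be evaluated at 1 hr, 2 hr, 6hrs, 24hrs, 48hrs, 72hrs".
- **Assessments**: "Patients will be called at 3, 6, and 12 months post operatively to fill out a chronic pain survey".
- **Inclusion criteria**: "All patients undergoing partial mastectomy procedures", with an age range of 18 to 75.
- **Exclusion criteria**: the entry closest to existing pain is "Daily use of opioid for more than three weeks". It is a medication criterion; no entry names pain itself.
- **Outcome Measurements**: cut-points may be set once the score distributions have been examined. One stratification variable refers to a preoperative pain modality. It is not defined, and no item in the data list corresponds to it.

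**The concern.** Postoperative chronic pain means pain that surgery caused or made worse. A single score at 3, 6 or 12 months does not show that. A patient with long-standing back or joint pain, or pain from earlier breast surgery, who does not take opioids daily is eligible and may score above zero at every follow-up whatever the operation did. A pain disability index measures how far pain limits the patient and, as listed, is not tied to the operated side.

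Three things are at stake. A reported rate of chronic postoperative pain would mix old pain with new pain in unknown proportions. Variation between patients that a baseline score could explain stays in the residual. And if the arms differ by chance in prior pain, nobody will be able to see it or adjust for it. None of this can be repaired later, because a baseline cannot be measured after surgery.

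**Working it through.** **Step 1. Is there a baseline anywhere?** The three places that schedule pain measurements agree. In Treatment technique, Assessments and the Data collection list, acute scores start 1 hour after surgery and the chronic-pain survey starts at 3 months. Two items might stand in for a baseline. The preoperative pain modality variable is undefined and may mean the analgesic technique. Outpatient notes are a listed data source and may mention earlier pain, but they are not a standardized score on the follow-up scale. Neither fills the gap.

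**Step 2. Plan figures.** The plan gives no sample size, effect or event rate for chronic pain, so there is no figure to reproduce. The 112 patients (56 per group) were set for opioid use. I take from the plan only n = 56 per arm, alpha 0.05 (treated as two-sided, which the plan does not state) and 80% power. All other inputs below are assumptions.

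**Step 3. Precision.** The detectable difference without adjustment is (1.960 + 0.842) × √(2/56) = 2.802 × 0.189 = 0.53 SD. Adjusting for a baseline that correlates r with follow-up multiplies residual variance by 1 − r² and the detectable difference by √(1 − r²).

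| Assumed r | Variance removed | Detectable difference |
|---|---|---|
| 0.3 | 9% | 0.529 × 0.954 = 0.505 SD |
| 0.5 | 25% | 0.529 × 0.866 = 0.46 SD |
| 0.6 | 36% | 0.529 × 0.800 = 0.42 SD |

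**Step 4. Reported rates, if the index is dichotomized.** Let q be the share of patients whose prior pain persists to follow-up, and assume new pain in 25% (control) and 15% (block) of the others. The observed rate is q + (1 − q) × new rate.

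| q | Control | Block | Ratio | Difference | Old pain among control / block cases |
|---|---|---|---|---|---|
| 0 | 25% | 15% | 0.60 | 10 points | 0% / 0% |
| 0.1 | 32.5% | 23.5% | 0.72 | 9 points | 31% / 43% |
| 0.2 | 40% | 32% | 0.80 | 8 points | 50% / 62.5% |
| 0.3 | 47.5% | 40.5% | 0.85 | 7 points | 63% / 74% |

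The last column is q divided by the observed rate.

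**Step 5. Chance imbalance.** If the prevalence of prior pain is p, the standard error of the difference in prevalence between arms is √(2p(1 − p)/56). By the normal approximation, the chance of a gap of at least 10 points in either direction is about 8% for p = 0.1, 19% for p = 0.2 and 25% for p = 0.3.

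**The case against.** The strongest reply is that the trial is randomized. Prior pain is balanced in expectation, so comparing the 3-, 6- and 12-month index between arms is valid without a baseline, and chance imbalance is already covered by the type I error rate. This stands. A reader might infer that the comparison is biased or that the objective cannot be answered at all; the documents support neither. The objective is worded as observation, while the other secondary objectives ask whether the block produces a result.

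Other parts of the reply also stand:

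- The survey text is not in the documents. It may ask about site or onset, so it would be too strong to say that old and new pain can never be told apart. No such item is described, though, and recall months later is weaker than a score taken beforehand.
- It would be wrong to say that patients enter whatever their existing pain. The daily-opioid exclusion probably removes some of the more severe cases.
- Step 4 assumes a yes/no outcome and that prior pain persists. The plan only permits cut-points, and the absolute difference shrinks less than the ratio does.
- A baseline would not make the objective confirmatory. For 25% versus 15% with no prior pain, the standard error is √((0.1875 + 0.1275)/56) = 0.075. Power is then about Φ(0.10/0.075 − 1.96), or 27%.

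A reader might also extend the point to acute pain and opioid use, on the ground that baseline pain predicts both. The documents give nothing to support that, and the primary outcome is not in question here.

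What the reply does not answer is interpretation. Randomization protects the contrast between arms, but it does not make a rate of chronic postoperative pain in either arm meaningful.

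**Conclusion.** The point holds within limits. The plan measures chronic pain only after surgery, admits patients with existing pain who are not long-term daily opioid users, and has no standardized baseline. The randomized comparison of the index remains unbiased on average. The losses are in classifying pain as new or worsened, in interpreting any reported rate, in precision, and in seeing or adjusting for a chance imbalance.

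The gain in precision is modest: from 0.53 SD to about 0.50 SD at an assumed correlation of 0.3, or 0.46 SD at 0.5. The effect on reported rates could be larger. Under the assumptions of Step 4, between 31% and 74% of counted cases would be old pain, depending on the arm and on whether q is 10%, 20% or 30%. These figures illustrate the size of the problem and do not predict it, since the documents give no prevalence, event rate or correlation. This affects one descriptive secondary objective. It should be fixed because the fix is cheap and the information cannot be recovered later.

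**What to change.** 1. After consent and before the random draw in the preoperative area, give the same pain disability index and one 0-10 item for pain in the operative breast or axilla.
2. Repeat the site item at 3, 6 and 12 months, and add all of these to the Data collection list.
3. Analyze the index at 3, 6 and 12 months adjusted for its baseline value.
4. Report chronic postoperative pain as new or worsened relative to baseline, and state before looking at the data what counts as worsened.
5. Leave eligibility unchanged and keep the objective descriptive.

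The cost is a few minutes of patient time, one extra item at each follow-up call and one covariate. The consent contact already takes place, preferably through REDCap, and Enrollment procedures says that patients consented on the day arrive several hours before surgery. The primary analysis and sample size do not change.

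### The only measure named for chronic postoperative pain at 3, 6 and 12 months is a disability index; presence, site and intensity of surgical-site pain are not specified

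*Combined protocol and SAP*

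**What the plan says.** All references are to the combined protocol and SAP.

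- **Secondary Objectives, item 4:** "To observe the effect on chronic postoperative pain in patients who have breast surgery".
- **Treatment technique (follow-up paragraphs):** "At 3 months, 6 months, and 12 months patients will be called to answer a survey with regards to chronic pain". The survey is not named.
- **Assessments:** "Patients will be called at 3, 6, and 12 months post operatively to fill out a chronic pain survey". Again the survey is not named and its items are not listed.
- **Data collection (under Benefits):** "Chronic pain (pain disability index) at 3, 6, 12 months". This is the only place where a chronic pain instrument is named.
- **Pain intensity:** Assessments states "Patients will be asked to rate their pain on scale of 0-10" in connection with the contacts up to 72 hours. Treatment technique gives the times as "scores will be evaluated at 1 hr, 2 hr, 6hrs, 24hrs, 48hrs, 72hrs", and Data collection gives "VAS Score at 1, and 6, 24, , 48, , and 72 hours after surgery". The two lists differ on the 2-hour score, which does not matter here. Both end at 72 hours.
- **Outcome Measurements:** no definition of a chronic pain case and no analysis specific to this objective. The section only leaves open categorising scores once their distributions have been examined.

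**The concern.** The objective is about pain after surgery, while the one named instrument is, by its name, an index of disability due to pain. These are related but different quantities. A patient may have pain at the operated breast that does not limit activity, or be limited by pain that has nothing to do with the operation. Unless the call ties the answers to the operated site, a disability score may not separate such patients from those with disabling surgical-site pain.

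At stake is what can be reported after a year of follow-up. With only the named measure, the trial could compare pain-related disability between arms. It could not state what proportion of each arm has chronic pain at the surgical site, or how intense that pain is. Items not asked at the 3-month call cannot be recovered later.

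**Working it through.** The plan gives no figure for this objective, so there is nothing to recompute. The check sets the relevant sections side by side.

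**1. What is specified, and when**

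| Quantity | Up to 72 hours | 3, 6 and 12 months |
|---|---|---|
| Pain intensity, 0-10 or VAS | Yes (Treatment technique, Assessments, Data collection) | Not specified |
| Presence of pain, yes/no | Obtainable from the intensity score | Not specified |
| Pain at the operated site | Not specified | Not specified |
| Disability from pain | Not specified | Pain disability index (Data collection) |
| Definition of a chronic pain case | Not applicable | Not specified |

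**2. Is the index the same thing as the unnamed survey?** The follow-up text describes three surveys: quality of recovery and OBAS at 72 hours, and a chronic pain survey at 3, 6 and 12 months. The Data collection list has three matching entries at the same times, and the third is the pain disability index. The natural reading is that the index is the chronic pain survey. Treatment technique cites an appendix for the first two surveys but none for the third, so nothing in the text points to further items.

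**3. What can be derived from the specified items?** A rate of chronic surgical-site pain needs presence and site. An intensity comparison needs a score at that site. Neither is specified after 72 hours, so neither quantity follows from the plan as written. What does follow is a disability score by arm at three times.

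**4. How might unrelated pain enter?** The inclusion and exclusion criteria do not exclude patients with pain elsewhere; the nearest exclusion is daily opioid use for more than three weeks. Randomisation makes unrelated pain similar in the two arms on average. The expected consequence is therefore added noise and possibly a diluted difference, not a systematic advantage for one arm. The documents give no prevalence of unrelated pain and no scoring rule for the index, so the size cannot be calculated.

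**5. How much contact is already planned?** 3 calls × 112 patients = 336 calls at most. This counts the calls at which the missing items could be asked. It does not measure error.

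**The case against.** The strongest reply is that the survey form cannot be seen. Data collection introduces its list with "In addition to the surveys used to measure subjective and objective outcome, other data will be collected during patient interviews including", so the list is additional to the surveys and not exhaustive on its face. The survey appendix is not in the available text either. The form used at the calls may already ask about site and intensity, and the documents do not describe the items or scoring of the index. This stands. A reader might infer that presence and intensity of pain will not be recorded at all; the documents support only that they are not specified.

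Second, disability is a legitimate facet of chronic pain, and the objective is only to observe an effect. It does not appear among the secondary hypotheses and sets no target rate. This also stands. A reader might infer that the objective cannot be answered, but an index of pain-related disability gives partial, indirect information on it.

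Third, the comparison is randomised, so a between-arm difference in the index remains interpretable as a difference in pain-related disability. That is correct and limits the consequence to noise, dilution and indirectness. It does not turn the index into a rate or an intensity of surgical-site pain.

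Fourth, Assessments has complications logged from consent through the final contact, and the adverse event definition is broad enough to catch some persistent pain. This is partial cover: event reporting is not a systematic question put to every patient at fixed times.

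**Conclusion.** The point holds in a limited form. The pain disability index is the only measure named for the chronic pain objective, and no item on presence, site or intensity of pain at the operated site is specified at 3, 6 or 12 months. As specified, the follow-up informs the objective indirectly and yields no rate or intensity of chronic surgical-site pain by arm.

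The conclusion rests on two assumptions. The first is that the index is the chronic pain survey, which the matching times suggest but the text does not state outright. The second is that the index measures disability, which is taken from its name alone. If the form already contains the missing items, the remaining defect is that the protocol neither lists them nor defines the endpoint.

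No numerical size can be given. The point is minor and confined to one secondary, observational objective. The primary outcome, total opioid use, and the sample size of 112 are not affected.

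**What to change.** Keep the pain disability index. State in the protocol what the 3, 6 and 12 month survey contains. Unless the form already has them, add two questions to those calls:

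1. Is there pain at the operated breast, axilla or same-side arm (yes/no)?
2. If yes, how strong is it on the 0-10 scale already used up to 72 hours?

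Define chronic postoperative pain from these two items before follow-up data are examined, report its rate and intensity by arm at each time, and report the index as the impact of that pain.

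The cost is about a minute per call, at calls already planned. No visit, treatment or sample size changes. If the form already contains the items, the cost is only the added protocol text.

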## **2. Synopsis and Medical Application:**

### **Specific Aims:**

#### **Primary Hypothesis:**

A pectoralis 1 and 2 block with liposomal bupivacaine will result in decreased total opioid usage relative to bupivacaine infiltration after an elective partial mastectomy

**Secondary Hypotheses:** A pectoralis 1 and 2 block with liposomal bupivacaine will result in improved quality of recovery score, decreased maximal pain scores, and decreased rate of conversion to general anesthetic.

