### **Enrollment procedures:**

Patients will be recruited from the group of adult surgical patients at the University of Minnesota undergoing partial mastectomy procedures. Patients will be approached in either the surgeon's clinic or pre-assessment clinic by a research staff member to determine their interest in participation. Subjects interested in the study will be presented with consent and Health and Insurance Portability and Accountability Act (HIPAA) forms, with the REDCap e-consent process being preferentially used. The patient will review the forms with the surgeon, anesthesiologist or other study staff. Subjects will be reminded that participation is completely voluntary, and that they may stop participation at any time without question or penalty. The surgeon or anesthesiologist will answer any questions that the subjects may have about the study. If the patient decides to participate, they will be asked to sign the consent and HIPAA forms. One copy will be saved for study records, and the subject will be provided with a copy of the forms for their own records. If they need additional time to consider enrollment, they will be asked if we can reach out to them by phone the night before surgery or if we should revisit the study with them on the day of surgery. If the patient is unable to be consented prior to day of surgery, the research staff will approach them in the preoperative surgical area. These patients will have significant time to review the study with research staff as well as the physicians performing the procedure due to the fact they arrive several hours prior to their scheduled surgery. All subjects will have enough time to ask questions about the study and the potential risks involved regardless of which venue they are consented. Any patient that refuses to participate in the study at any time point will be placed on a secured list to avoid duplicate attempts to recruit them. All forms will be locked and stored in a file cabinet in the research department. Enrolling consecutive patients will help reduce selection bias. Any patient who does not complete all necessary paperwork and answer questions at the appropriate time intervals will be eliminated from the study. Patients lost to follow-up, or patients who decide not to participate in the study after initial enrollment, or patients who are eliminated from the study for any reason will have their study records shredded and will not be included in the final data-analysis.

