### **Outcome Measurements:**

Outcome measures include both clinical assessments and subjective outcome measures reported by the subject on different rating scales.

Distribution of the scores and the clinical evaluations will be examined and cut-points may be assigned to create categorical data. Statistical analysis of parametric data will be done using ANOVA techniques with corrections for repeated measures (when necessary); non-parametric data will be analyzed with Chi-squared techniques. Statistical significance will be defined as  $p < 0.05$ . Power is expected to be 0.8. Data stratification will be done where appropriate. Stratification variables include: pre-operative pain modality.

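### The 80% power is tied to 112 enrolled patients with no allowance for loss, while the enrollment rules remove incomplete patients from the analysis, including some who could have a usable opioid total

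*Combined protocol and SAP*

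**What the plan says.** **Power.** Statistical Considerations names total opioid use as the primary outcome and states: "A sample size of 112 (56 per group) will be enrolled in order to power our study at 80" percent, "to detect a 35% decrease in total post-operative opioid usage for our treatment group versus the control", at an alpha of 0.05. On the source of the number it says: "This sample size was estimated based on previous estimates for postoperative analgesic consumption from similar trials", and cites a meta-analysis. It gives no control mean, SD, test, sidedness, evaluable number or loss allowance. Outcome Measurements repeats: "Power is expected to be 0.8".

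**Removal from the analysis.** Enrollment procedures states: "Any patient who does not complete all necessary paperwork and answer questions at the appropriate time intervals will be eliminated from the study". The sentence after it extends this to patients who are lost to follow-up, who withdraw, or who are eliminated for any reason. Their study records are to be shredded and they do not enter the final analysis. No replacement of such patients is described.

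**Contacts.** The follow-up text under Treatment technique lists pain assessments at 1, 2, 6, 24, 48 and 72 hours, daily opioid use, two surveys at 72 hours, and chronic pain calls at 3, 6 and 12 months. Assessments says data collection runs to postoperative day 3 and describes the later calls as additional contacts.

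**Form of the outcome.** Outcome Measurements says that, after distributions are examined, "cut-points may be assigned to create categorical data". It refers to scores and clinical evaluations and does not mention opioid use.

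**The concern.** The number that carries the 80% is the number enrolled. The number that enters the test is smaller by however many patients the elimination rule removes, and the plan does not connect the two. Every removal lowers power.

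The rule is also broader than the primary outcome needs. A patient can have a complete opioid record to 72 hours and still be removed for a missed form. Because the relevant time intervals are not defined, a missed 12-month call could have the same effect. The analysis would then discard primary data already in hand, and would do so after randomization, on grounds that may be related to how the patient fared.

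Two things are at stake. A null result could be read as coming from a trial with 80% power when the analyzed number supported less. And once records are shredded, nobody can later check whether the removed patients differed between groups.

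**Working it through.** **Inputs from the protocol.** 56 per group, alpha 0.05, power 80%, 35% relative decrease (Statistical Considerations).

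**Not in the protocol, assumed here.** A two-sided comparison of two means; 112 *analyzed* patients giving exactly 80%; loss equal in the two groups; loss rates of 5% to 20%. The primary hypothesis is worded in one direction ("will result in decreased total opioid usage relative to bupivacaine infiltration after an elective partial mastectomy"), but no one-sided test is stated.

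**Step 1: can 112 be reproduced?** Not directly, because no mean or SD is given. It can only be solved backwards:

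- d = (z₀.₉₇₅ + z₀.₈₀) × √(2/n) = (1.960 + 0.842) × √(2/56) = 0.529. With the t distribution, d = 0.534.
- For a 35% decrease, the implied SD as a fraction of the control mean is 0.35/0.529 = 0.66 (t: 0.655).

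This shows only what the plan must have assumed if 112 is the analyzed number. It does not confirm the 112.

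**Step 2: power after removal.** With n = 56 × (1 − loss), power = Φ(d × √(n/2) − 1.960). At 10% loss, n = 50.4 and 0.529 × √25.2 − 1.960 = 0.70, so power is 75.7%.

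| Share removed | Analyzed per group | Power, normal approximation | Power, t-test |
|---|---|---|---|
| 0% | 56.0 | 80.0% | 80.0% |
| 5% | 53.2 | 78.0% | 77.9% |
| 10% | 50.4 | 75.7% | 75.7% |
| 15% | 47.6 | 73.3% | 73.2% |
| 20% | 44.8 | 70.7% | 70.5% |

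**Step 3: how much rests on the missing SD?** With all 56 per group analyzed (normal approximation):

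| SD / control mean | Power |
|---|---|
| 0.5 | 95.9% |
| 0.6 | 87.0% |
| 0.7 | 75.4% |
| 0.8 | 63.9% |
| 1.0 | 45.7% |

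The unstated ratio moves power more than any loss rate in Step 2.

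**Step 4: could an allowance already be inside the 112?** If 112 already allowed for 10% loss, the implied ratio would be 0.63; for 20% loss, 0.59 (normal approximation). Nothing in the text separates these from 0.66.

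**The case against.** **The 80% may survive the losses.** Without an SD or a loss rate, nobody can show that the design falls short. If the SD were 0.60 of the control mean, the t-test would have 86% power with no loss and still 80% after 15% loss. An allowance could also be built into the 112 without being mentioned. This stands. A reader might infer that the trial does not deliver 80%, or that its arithmetic is wrong; the documents support neither. What remains is that the statement is tied to enrollment, shows no allowance, and cannot be checked.

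**The elimination rule may mean only the first 72 hours.** Assessments ends data collection at postoperative day 3 and calls the later calls additional, so the narrow reading is at least as plausible. This also stands: the 12-month reach is one of two readings. Even so, the narrow reading still removes a patient with a complete opioid total for a missed survey at 72 hours.

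**The plan acts against loss.** Data collection describes coordinator checks and monthly meetings to secure follow-up. These may keep losses small, and about 4.9% loss costs only 2 points of power. They are not an allowance, and Enrollment procedures itself expects some patients to be lost.

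**Cutting the outcome.** A reader might infer that the cut-points in Outcome Measurements bring the power of the primary test far down. At the implied d, on a normal model, a two-category split of opioid use would give about 46% to 60% with all 112 analyzed. But the text is optional and does not name opioid use. The figure also depends on the assumed distribution: for lognormal use with an SD/mean ratio of 0.655 in both groups, a median split has about 83% power. So this is no estimate of the trial's power; it is only a reason to exempt the primary outcome explicitly.

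**Post-surgical exclusions.** The exclusion criteria include "Patients who remain intubated overnight after surgery or who are unable to provide information regarding their pain immediately postoperatively", which can be known only after surgery. The documents give no sign that this would remove many patients, and the point does not rest on it.

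**Conclusion.** The concern holds in a conditional form. The protocol attaches 80% power to 112 enrolled patients, states no loss allowance, and has a rule that removes patients from the analysis for reasons unrelated to whether their opioid total is known. If 112 analyzed patients are what gives 80%, then 5%, 10% or 20% loss leaves about 78%, 76% or 71%. Those figures rest on a two-sided comparison of means, a back-solved d of about 0.53, and loss rates that the documents do not supply.

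The direction is certain: each removal lowers power. The actual level is not known and could be above or below 80%, because the control mean, SD and test are missing. The elimination rule is the more important defect, since it discards usable primary data and can be changed at little cost.

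**What to change.** 1. **Enrollment procedures.** Replace the elimination rule. Every randomized patient with a 72-hour opioid total stays in the primary analysis, in the assigned group, whatever other forms or later surveys are missing. (Statistical Considerations gives no time window for the total; 72 hours is taken here because daily opioid use is recorded to that point.) Retain data already collected instead of shredding it, as consent allows.
2. **Statistical Considerations.** State that the 80% applies to 112 analyzed patients, if that is what was calculated. Give the control mean, SD, test and sidedness used, and the power at a stated loss rate. If an allowance was already included, say so and give the evaluable number. The percentages above should not be copied in; they are back-solved and should be recomputed from the sponsor's own inputs.
3. **Outcome Measurements.** Specify that total opioid use is analyzed uncut, by one named continuous or rank-based method, and that the optional cut-points do not apply to the primary outcome.

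**Cost.** No patients are added. The stated power becomes slightly less favorable, and the analysis-set and record-retention text must change, so this is more than a rewording of the power sentence.
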